4.6 Handling of Missing Data

By definition, all subjects in the PP population will have sufficient data required to determine primary endpoints. In instances where some (but not all) of the data is missing, two situations are possible: 1) some data are not available but the data that is available indicates for certain the patient is a failure, and 2) the data that is available indicates a possible cure and nothing indicates a failure, but without complete data it is not possible to determine for certain it is indeed a cure. Thus, a patient with situation 1) will be considered evaluable, while a patient with situation 2) will be non-evaluable and thus not included in the PP population. Any patients with all data missing will also be non-evaluable.

For subjects who are not eligible for inclusion in the PP populations but who are eligible for inclusion in the mITT subject populations, all missing data will be imputed as worst-case scenario outcome (e.g. failure).

If adverse event start dates are missing or incomplete, the following rules will apply for determining if an event is to be considered treatment emergent. If start date is completely missing, start date will be set as same day as start of treatment and assumed to be at a time following subject's first dose. If start date is incomplete, the date closest to start of treatment will be assumed, without compromising the incomplete data available for the start date.

If study medication start dates are missing or incomplete, the following rules will apply for determining inclusion in the Safety population. If the start date is completely missing and there is no documentation indicating that the patient used study medication, the date will be left as missing and the patient will be excluded from the Safety population. If the start date is completely missing or incomplete and there *is* documentation that indicates the patient used study medication, the date will be imputed to the earliest date and time post-randomization that is consistent with the partial data, and the patient will be included in the Safety population.

4.7 Efficacy Analyses

4.7.1 Primary Efficacy Analysis

The primary efficacy endpoint is the cure rate at the test-of-cure visit (Visit 2). Definitions of cure for each of the three infection studies are provided in [Section 4.3](#).

Subjects in all studies will be categorized as cure or failure for the mITT analyses, and as cure, failure or non-evaluable for the PP analysis. The number and percentage of subjects in each treatment group in each of these categories will be reported. Separate statistical analyses will be performed for each of the three infection studies. All treatment comparisons will be based on two-tailed 0.05 significance level hypothesis tests and 95% confidence intervals for the difference in proportion of successes in each treatment. The primary comparison of treatment groups for each study will be performed using a continuity corrected Chi-squared test and Wald continuity corrected confidence intervals. It is anticipated that in some treatment groups in one or more of the infection studies, there may not be sufficient expected cell counts for the Chi-squared test and confidence intervals based on the normal approximation to be

accurate. Therefore, if all expected cell counts are not at least 5, Fisher's Exact test and confidence intervals using the method of Chan and Zhang (1999) will be used.

The primary efficacy analysis for each of the three infection studies will be performed using the mITT population with worst case scenario imputation for missing data. Supportive analyses will also be conducted using the PP population.

Efficacy analysis will not be done for the ITT population, as subjects in the BV and Mixed studies who do not have a gram stain ≥ 4 , or subjects in the VVC and Mixed studies who do not have a positive yeast culture, are not evaluated for efficacy. These subjects do not return for Visit 2; rather, they have the Limited Termination visit for safety evaluations only.

BV Study: The primary statistical objective of the BV infection study is to demonstrate the superiority of BV Gel to Placebo Gel in the treatment of BV. The assessment of superiority will be performed by conducting a continuity corrected Chi-squared test for a difference in the proportion of BV cure between the two treatments. Also, a 95% two-sided confidence interval for the difference in proportion of BV cure between the two treatments will be constructed.

VVC Study: The primary statistical objective of the VVC infection study is to demonstrate the superiority of VVC Gel to Placebo Gel. The assessment of superiority will be performed by conducting a continuity corrected Chi-squared test for a difference in the proportion of VVC cure between the two treatments. Also, a 95% two-sided confidence interval for the difference in proportion of VVC cure between the two treatments will be constructed.

Mixed Infection Study: The primary statistical objective of the Mixed Infection Study is to demonstrate the superiority of the Combo Gel to both BV Gel and VVC Gel. The assessment of superiority will be performed by conducting a continuity corrected Chi-squared tests for a difference in the proportion of Mixed Infection cure between the Combo Gel and each of the two single entity treatments. If the P-values for both of the hypothesis tests are less than or equal to 0.05, the Combo Gel will be considered superior to both of the single entity gels. Despite there being two comparisons made within the same study, no adjustment for multiplicity is necessary since both comparisons must be positive instead of "at least one," in order to conclude superiority of the Combo Gel. Also, 95% two-sided confidence intervals for the difference in proportion of Mixed Infection cure between the Combo Gel and each of the two single entity treatments will be constructed.

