4.2 Analysis Populations

The primary assessments of efficacy will be based on the modified intent-to-treat (mITT) population. In addition to the mITT analyses of the data, analyses will also be conducted on the per protocol (PP) population. The data analysis populations are defined as:

- ITT: The intent-to-treat population will include all subjects randomized to treatment.
- mITT: The modified intent-to-treat population will include all subjects randomized to treatment and administered at least one dose of study drug. Subjects who are Lost to Follow-up and for whom there is no documentation to ascertain whether or not they were administered treatment will be excluded from the mITT population.
 - In addition, to be included in the mITT population subjects in the VVC and Mixed Infection studies must have a positive baseline vaginal fungal culture for *Candida* species. Subjects in the BV and Mixed Infection studies must have a Gram stain Nugent score of ≥ 4 at the baseline visit.
 - Subjects randomized to treatment but whose baseline laboratory tests subsequently reveal positive results for *Trichomonas vaginalis*, *Chlamydia trachomatis*, and/or *Neisseria gonorrhoeae* will be excluded from the mITT population.
- PP: The per protocol population will include the subset of mITT subjects that had no major protocol violations and who are classified as efficacy evaluable with no missing data required to determine primary endpoints. Major protocol violations likely to bias assessment of the primary endpoint for the per protocol population will be determined prior to unblinding the data.
- Safety: The safety population will include all subjects randomized to treatment and administered at least one dose of study drug.

Major protocol deviations (i.e. deviations likely to bias assessment of the primary efficacy measure) that will be used to assess inclusion in the PP population will be determined and reviewed by the Sponsor prior to unblinding the data.

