4.5 Determination of Sample Size

Approved labeling, clinical data included in New Drug Applications and approval packages, and sponsor experience with the compounds in this study and similar therapies provide the following estimates and ranges of the cure rates (as proportions) for the treatments within each infection study.

1. BV Subjects
 - a. BV Gel (0.9% metronidazole gel): .50 (.45-.55)
 - b. Placebo Gel: .20 (.15-.25)
2. VVC Subjects
 - a. VVC Gel (0.8% terconazole gel): .70 (.65-.75)
 - b. Placebo Gel: .20 (.15-.25)
3. Mixed Infection Subjects
 - a. Combo Gel (0.9% metronidazole gel and 0.8% terconazole gel): .35 (.30-.40)
 - b. VVC Gel (0.8% terconazole gel): .10 (.05-.15)
 - c. BV Gel (0.9% metronidazole gel): .10 (.05-.15)

Under the assumption that the above estimated cure rates are true for the population, sample sizes were calculated for each infection study based on these estimates for at least 90% power and at least 50 subjects per treatment group. Superiority tests will be performed as two-sided, $\alpha = 0.05$ level significance tests, and sample sizes were calculated using Fisher's Exact test in case the planned Chi-squared test is not appropriate.

The following table provides the sample size required for each treatment group within each infection study. The total sample size is given, and represents the number of evaluable subjects required (Per Protocol population). Entry in each infection study of the trial will be stopped when this number of evaluable subjects is reached, since evaluable/not-evaluable can be determined from the completed case report form prior to unblinding.

Required Number of Evaluable Patients, by Infection Study and Treatment Group							
Study:	BV Only Patients		VVC Only Patients		Mixed Infection Only Subjects		
Treatment Arm:	BV Gel	Placebo Gel	VVC Gel	Placebo Gel	BV Gel	VVC Gel	Combo Gel
Expected Cure Rate	50%	20%	70%	20%	10%	10%	35%
n for at least 80% Power, and at least 50 per group	58	58	50	50	63	63	63
Actual Power	90.0%		> 99.9%		90%		
Total N	405						

Thus, subjects will be enrolled until approximately 405 evaluable subjects, as indicated above, for all three infection studies, have completed the trial.

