14.1 Demographic and Study Conduct Summaries

Table 14.1.1	Summary of Subject Disposition, All Randomized Subjects
Table 14.1.2	Summary of Subject Accounting, All Randomized Subjects
Table 14.1.3	Summary of Major Protocol Violations, All Randomized Subjects
Table 14.1.4	Summary of Inclusion/Exclusion Criteria Not Met, All Randomized Subjects
Table 14.1.5	Summary of Demographic and Baseline Characteristics, mITT Population
Table 14.1.6	Summary of Contraceptive and Obstetric Status, mITT Population
Table 14.1.7	Summary of History of Gynecologic Infection, mITT Population
Table 14.1.8	Summary of Infection Medications, mITT Population
Table 14.1.9	Summary of Past Medical and Surgical History, mITT Population
Table 14.1.10	Summary of Current Medical and Surgical History, mITT Population
Table 14.1.11	Summary of Baseline Vital Signs, mITT Population
Table 14.1.12	Summary of Baseline Physical Exam, mITT Population
Table 14.1.13	Summary of Baseline Symptom and Sign Severity Score, mITT Population
Table 14.1.14	Summary of Baseline Pelvic Exam, mITT Population

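### The valid but unadjusted primary comparison makes no use of the baseline severity and Nugent scores; a prespecified adjusted risk difference would add modest precision, mainly in the Mixed Infection Study

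*SAP*

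**What the plan says.** SAP section 4.7.1 sets one method for all three studies: "The primary comparison of treatment groups for each study will be performed using a continuity corrected Chi-squared test", with a Wald interval for the difference in cure proportions. If any expected cell count is below 5, Fisher's Exact test and the Chan and Zhang interval replace them. The same section adds that "All treatment comparisons will be based on two-tailed 0.05 significance level hypothesis tests" and makes the mITT population, with missing outcomes counted as failures, primary. In the Mixed Infection Study, Combo Gel must beat each single gel at p ≤ 0.05. No covariate, stratum or adjusted sensitivity analysis is named.

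Two baseline scores are available. Section 3.1 has itching, burning, irritation, edema, erythema and excoriation each rated 0 to 3 at Visit 1, and requires a total above 2 for entry to the VVC and Mixed studies. Section 4.2 says that BV and Mixed subjects "must have a Gram stain Nugent score of" at least 4 at baseline to be in the mITT population. Beyond eligibility, the scores appear in baseline summaries, such as Table 14.1.13 in section 14.1 ("Summary of Baseline Symptom and Sign Severity Score, mITT Population"), and in secondary change-from-baseline analyses.

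**The concern.** VVC cure (section 4.3) is resolution of all signs and symptoms attributable to VVC. The severity score is close to a baseline measurement of the same thing, so a subject who enters with more to resolve may be less likely to be cured. The link from baseline Nugent score to BV clinical cure is less direct but plausible. Mixed cure requires both cures, so both scores are candidates there.

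Two things are at stake. First, outcome variation that a baseline score explains stays in the error term. Second, with 50 to 63 subjects per arm a prognostic score can differ between arms by chance. The baseline tables will show such a difference, but the plan fixes no analysis that responds to it, so any adjustment would be chosen after the data are seen.

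**Working it through.** **Inputs (SAP sections 4.5 and 4.7.1).** Two-sided α = 0.05. Mixed: 63 per arm, cure rates 0.35 (Combo), 0.10 and 0.10. BV: 58 per arm, 0.50 and 0.20. VVC: 50 per arm, 0.70 and 0.20. Mixed success needs both p-values ≤ 0.05. The documents give no association between either score and cure, so that is assumed over a range.

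**Step 1: reproduce the stated power.** Section 4.5 sizes with Fisher's Exact test. Exact power is Σₓ Σᵧ Bin(x; n, p₁) Bin(y; n, p₂) · 1{p-value ≤ 0.05}.
- Mixed, one comparison: 90.6% (stated 90%).
- BV: 90.6% (stated 90.0%).
- VVC: 99.94% (stated > 99.9%).

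The planned corrected Chi-squared test with its Fisher fallback also gives 90.6% for Mixed and for BV.

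**Step 2: joint power in Mixed.** The two comparisons share the Combo arm and the single-gel rates are equal, so joint power is Σₓ Bin(x; 63, 0.35) · [Σᵧ Bin(y; 63, 0.10) · 1{significant}]².
- Planned test: 84.4%. Fisher throughout: 84.5%.
- Same data, no continuity correction and no covariate: 89.1%, which is 89.1 − 84.4 = 4.7 points more.
- Planned test elsewhere in the SAP's own ranges: 63.6% at 30/10/10 and 53.4% at 35/15/15.

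**Step 3: the covariate's own share.** The fair comparator for an adjusted test without continuity correction is the uncorrected unadjusted test. Simulation: 20,000 trials per row, 63 per arm, 35/10/10, one standard normal score with the same logistic slope in each arm, linear covariate-adjusted test.

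| Assumed log-odds per SD | R², single-gel / Combo arm | Joint power, uncorrected | Joint power, adjusted | Gain (points) |
|---|---|---|---|---|
| 0 | 0 / 0 | 89.2% | 89.0% | −0.2 |
| 0.3 | 0.008 / 0.020 | 88.6% | 89.1% | +0.5 |
| 0.5 | 0.023 / 0.051 | 89.0% | 90.1% | +1.1 |
| 0.8 | 0.059 / 0.116 | 89.1% | 91.9% | +2.8 |
| 1.2 | 0.129 / 0.212 | 88.7% | 93.9% | +5.2 |

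The simulation error of each power is about √(0.89 × 0.11 / 20,000) = 0.2 points. Logistic standardisation with one score (4,000 trials per setting) agrees: adjusted joint power 90.6%, 92.7% and 94.3% at slopes 0.5, 0.8 and 1.1. With two scores the gain was about 1 point or less at slopes 0 to 0.3, 2 to 3 points at 0.5 to 0.8, and 5 points at 1.1.

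At 30/10/10 the gain is larger at the steeper slopes. At 0.8 it is 75.6 − 71.3 = 4.3 points, but the result is still far below 90%.

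**Step 4: the other two studies.** BV power is 90.6% as planned and 93.3% uncorrected. An adjusted test at slope 0.5 gave 94.7%, so the covariate's share is 94.7 − 93.3 = 1.4 points. VVC has no power left to gain.

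**Step 5: error rate of the adjusted test.** At 10% against 10% with 63 per arm, 0.10 × 63 = 6.3 cures are expected per arm. Standardisation with plain influence-function standard errors then had one-sided type I error of about 2.5–3.1% with one score and 2.9–3.4% with two, against a nominal 2.5%. The planned corrected test had 1.1%.

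**Step 6: chance imbalance.** The difference in mean baseline score between two arms has standard error √(2/63) = 0.18 SD in Mixed and √(2/50) = 0.20 SD in VVC. In Mixed, a difference beyond 1.96 × 0.178 = 0.35 SD arises in about 5% of comparisons.

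**The case against.** The strongest reply is that nothing here is an error. The planned test is fully specified, valid under randomisation, matched by a risk-difference interval and in the same unadjusted family as the sizing method. Its type I error already allows for chance imbalance. That stands: a reader might infer that the primary analysis is biased or invalid without adjustment, and the SAP gives no support for this.

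A reader might also infer that leaving out the scores costs Mixed some 6 to 10 points of power, by setting the planned 84% beside an adjusted 90% to 94%. That contrast changes two things at once, and 4.7 points of it come from dropping the continuity correction. Nor do the missing covariates explain why Mixed falls below 90%. The sample size was set on one comparison while two must succeed, which is a separate issue, as is the difference between "based on these estimates for at least 90% power and at least 50 subjects per treatment group" in the text of section 4.5 and "n for at least 80% Power, and at least 50 per group" in its table. About 72 per arm would give 90% joint power with Fisher's test.

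It is also fair to object that the prognostic strength is assumed. The entry thresholds (severity above 2, Nugent at least 4) narrow both scores and may weaken prediction. Some of the apparent gain from plain standardisation reflects an error rate slightly above nominal, and two covariates with about six cures in an arm is a thin basis for a model. These objections limit the size and shape the fix. They do not remove the case for prespecifying an adjusted estimate: a useless score costs almost nothing (first row of the table), and the marginal risk difference remains the target.

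**Conclusion.** The point holds as an optional improvement in precision, not as an error. The primary comparison is valid but leaves unused two baseline scores that are already collected, one of which closely mirrors the VVC endpoint. In the Mixed study at 35/10/10, adjustment alone would add about 0 to 5 points to a joint power of about 84% under the planned test, over an assumed log-odds of 0 to 1.1 per SD; with weak prediction it is 1 point or less. The true figure cannot be computed from this document. BV meets its stated power and VVC far exceeds it, so for them the benefit is mainly a prespecified response to imbalance.

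The figures assume normal scores without entry truncation, a common slope across arms and exactly 63 subjects per arm. They ignore missing outcomes counted as failures and any mITT subjects beyond the evaluable number.

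**What to change.** Before unblinding, add to section 4.7.1 a baseline-adjusted marginal risk difference, standardised from a logistic model with treatment plus the severity score (VVC), the Nugent score (BV) or both (Mixed), in the mITT population with the same failure imputation.

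- **Inference:** use a small-sample-corrected standard error, or a randomisation-based p-value that follows the allocation scheme actually used. The plain influence-function version should not be used uncorrected.
- **Detail:** state the form of each score, and whether Mixed uses one three-arm model or one model per comparison.
- **Fallback:** reuse the plan's own rule. Any expected cell count below 5, or non-convergence of the model, reverts to Fisher's Exact test with the Chan and Zhang interval. With equal arms, the expected number of cures per arm is half the total, so the count rule on cures triggers below 10 cures across the two arms compared.
- **Minimum:** if the sponsor keeps the unadjusted test as primary, name the adjusted estimate as the key supportive analysis.

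The cost is a paragraph of SAP text and modest programming, with no added subjects. The downside is a model-based analysis that is harder to explain, with an unquantified benefit if the scores predict cure weakly. It does not replace reconciling the Mixed sample size with the requirement that both comparisons succeed.

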4.7.2 Secondary Efficacy Analyses

Secondary efficacy endpoints are listed in [Section 4.3](#). These endpoints include variables that are categorical (including binary variables), ordinal (such as rating scores), or time to event variables (such as time to resolution of symptoms). The analysis of the secondary endpoints will be performed using the mITT population with worst case scenario imputation for missing data, with supportive analyses conducted using the PP population.

For the secondary endpoints that are categorical or ordinal with four or fewer levels (including binary outcome variables), the analysis will include the proportion of subjects with each criteria or each score, at baseline and endstudy. The comparison of treatment groups will be performed using Chi-squared tests if all expected cell counts are at least 5, and Fisher's Exact test otherwise. For binary outcomes, (clinical outcome, mycological outcome, and eradication [or persistence] of individual fungal species) 95% two-sided confidence intervals for the difference in proportions will also be constructed using the continuity corrected Wald intervals when Chi-square tests are appropriate, or the method of Chan and Zhang (1999) otherwise.

Secondary endpoints that are ordinal data with more than four levels, such as Nugent score, the median score at baseline, endstudy, and the change from baseline will be computed, in addition to the proportion of subjects at each level. Treatment comparisons will be performed using the Wilcoxon Rank Sum test.

The secondary endpoint of time to resolution of symptoms will be analyzed in each infection study by arm using log-rank tests to compare arms within each study and Kaplan-Meier plots. Kaplan-Meier estimates of the quartiles for time to resolution will be computed, along with 95% confidence intervals. Censoring times for the Kaplan-Meier estimates will be based on the date of last contact or visit 3 (whichever is earliest) if symptoms never resolved or the patient was an early withdrawal and status is unknown.

The analysis of eradication (persistence) of individual fungal species will be conducted in subgroups of subjects defined by fungal species present at baseline (for the VVC and Mixed Infection studies).

In addition, for each study a summary will be made of subjects classified as:

- Persistent Infection – no cure at Visit 2 or Visit 3
- Persistent Cure – cure at Visit 2 and Visit 3
- Late Cure – no cure at Visit 2 but cure at Visit 3
- Recurrence – cure at Visit 2 but no cure at Visit 3

A descriptive analysis of the primary endpoint (cure rate) for BV subjects will be performed to assess the impact of loss of potency of the BV gel over time. The proportion of patients achieving a cure will be computed among cohorts of patients completing Visit 2 during each month the study was underway. These proportions will be tabulated by month for the BV Gel arms of the BV study and the mixed infection study. In addition, a plot of the proportions by month will be presented.

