3.1 Screening/Baseline Evaluations

Baseline (visit 1) medical evaluations will include:

- Medical and surgical history
- Contraceptive/obstetric status and gynecologic history
- Use of concomitant medications (i.e. current and within 30 days of enrollment) as well as treatments for BV and/or VVC infections within the past year
- Subject Assessment of Symptoms: Subjects will be asked to rate their current vulvovaginal symptoms of itching, burning, and irritation as absent=0, mild=1, moderate=2 or severe=3. The sum of the symptom score will be added to the vulvovaginal signs score obtained during the pelvic examination to determine a combined symptom and sign severity score.
- General physical examination and vital signs
- Laboratory tests
 - Urine pregnancy test for all women of child bearing potential
 - Papanicolaou smear (if subject is ≥ 21 years old and a Pap smear was not done within the past 3 years)
 - Tests for *Neisseria gonorrhoeae*, *Chlamydia trachomatis*, and *Trichomonas vaginalis*
 - Culture for *Herpes simplex* (only if suspected)
 - Vaginal culture for *Candida* species
 - Vaginal Gram stain

- CBC with differential and blood chemistries (i.e. BUN, Creatinine, ALT, AST, ALP, and bilirubin) for subjects enrolled in the Mixed Infection Study

Baseline (visit 1) pelvic examination and specimen collections will include:

- Visual inspection: rule out lesions caused by Herpes simplex virus or human papilloma virus (i.e. genital warts)
- Vulvovaginal signs rating: rate the degree of vulvovaginal edema, erythema, and excoriation as absent = 0, mild = 1, moderate = 2 or severe = 3. The sum of these ratings will be added to the vulvovaginal symptoms score given by the subject to determine a combined symptom and sign severity score. This total score must be > 2 in order to meet entry criteria for enrollment into the VVC or Mixed Infection study.
- Vaginal discharge characterization: By visual examination, characterize vaginal discharge in accordance with the descriptions below.
 - Normal/physiologic: normal discharge may vary in appearance and consistency depending on the menstrual cycle;
 - Abnormal: consistent with BV (i.e. off-white [milky or gray], thin, homogeneous discharge);
 - Abnormal: consistent with VVC (i.e. white, creamy, and curdy [cottage cheese like] adherent to the epithelium);
 - Abnormal: consistent with Mixed Infection (i.e. discharge of varying characteristics with relation to odor, color, and consistency)

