4.3 Efficacy Endpoints and Evaluations

The primary and secondary endpoints are reflective of each of the infection studies within the protocol. These include:

Primary Endpoints

- BV Study: BV cure rate, with cure defined as normal/physiologic discharge, negative whiff test, and < 20% clue cells (i.e. clinical cure)
- VVC Study: VVC cure rate, with cure defined as resolution of all signs and symptoms attributable to VVC (i.e. clinical cure)
- Mixed Infection Study: Mixed Infection cure rate, with cure defined as BV cure (i.e. BV clinical cure) AND a VVC cure (i.e. VVC clinical cure)

Primary efficacy endpoint evaluations will occur at the test-of-cure Visit 2.

If a subject requires additional treatment for vaginal discomfort/symptoms (i.e. a BV subject requiring treatment for BV, a VVC subject requiring treatment for VVC or a Mixed Infection subject requiring treatment for BV and/or VVC) prior to or at Visit 2, the subject will be considered a treatment failure. These subjects will be evaluable for the modified intent-to-treat (mITT) and the per-protocol (PP) population analyses, providing all other evaluability criteria for these population groups have been met.

Additionally, if a subject self-medicates herself for vaginal discomfort/symptoms at any time prior to Visit 2, the subject will be considered a treatment failure. If this occurs, the subject will remain evaluable for the mITT analyses but will be non-evaluable for the PP analysis.

Secondary Endpoints

Note, for BV a Gram stain Nugent score cure will be defined as a score of < 4, i.e. 0 – 3.

- BV Study: BV clinical and Gram stain Nugent score combined cure rate, and Gram stain Nugent score cure rate alone; changes/improvements in Amsel criteria and Nugent scores; time to resolution of symptoms
 - In addition, cure rates over time will be explored
- VVC Study: VVC clinical and mycologic cure rates combined and mycologic cure alone; changes/improvements in signs and symptoms scores; eradication (or persistence) of individual fungal species; time to resolution of symptoms
- Mixed Infection Study: BV clinical and Gram stain Nugent score cure rates alone and combined; changes/improvements in Amsel criteria and Nugent scores; VVC clinical and mycologic cure rates alone and combined; changes/improvements in signs and symptoms scores; eradication or persistence of individual fungal species; time to resolution of symptoms

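### SAP 4.7.2 sends short ordinal ratings to a Chi-squared/Fisher test that ignores severity order; if single 0-3 items are compared at a visit, the Wilcoxon test used for longer scores would suit better

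*SAP*

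**What the plan says.** Section 4.7.2 of the SAP sorts secondary endpoints into categorical, "ordinal (such as rating scores), or time to event variables (such as time to resolution of symptoms"), and then assigns tests by number of levels.

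- Four or fewer levels: the rule opens "For the secondary endpoints that are categorical or ordinal with four or fewer levels (including binary outcome variables"). It asks for "the proportion of subjects with each criteria or each score, at baseline and endstudy", and "The comparison of treatment groups will be performed using Chi-squared tests if all expected cell counts are at least 5", with Fisher's exact test otherwise. No trend or rank version is named.
- More than four levels, with the Nugent score as the example: medians at baseline and endstudy, the change from baseline, and the proportion at each level. "Treatment comparisons will be performed using the Wilcoxon Rank Sum test".
- Both rules apply under the same data convention: "The analysis of the secondary endpoints will be performed using the mITT population with worst case scenario imputation for missing data".

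Section 3.1 asks the clinician to "rate the degree of vulvovaginal edema, erythema, and excoriation as absent = 0, mild = 1, moderate = 2 or severe = 3". Sections 3.1 to 3.3 have the subject rate itching, burning and irritation on the same scale. The six ratings are added into a combined score. For the VVC study, section 4.3 lists the endpoint as "changes/improvements in signs and symptoms scores; eradication (or persistence) of individual fungal species"; the Mixed Infection study has the same scores endpoint.

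**The concern.** The plan picks the test by counting levels, not by asking whether the levels are ordered. A single 0-3 rating has exactly four ordered levels, so its level at a visit falls under the Chi-squared/Fisher rule. Those tests give the same p-value however the four categories are arranged. A significant result would show that the two distributions differ, not that severity is lower, and direction would have to be read from the tabulated proportions. For moderate shifts across all levels the test also has less power than the one the plan uses a paragraph later.

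What is at stake is small: secondary, item-level comparisons at a visit in the VVC and Mixed Infection studies, if any are made.

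**Working it through.** **1. Which endpoints does the short ordinal clause reach?** Cure, eradication and single Amsel criteria are binary. The discharge categories are unordered. The symptom sum and the sign sum each run 0-9, the combined score runs 0-18 (6 items × 3), and the Nugent score is the plan's own example of a longer scale; all of these go to Wilcoxon. Change in one item runs from -3 to +3, which is seven values, so it also goes to Wilcoxon. What is left is the level of a single 0-3 item at a visit.

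**2. Sample sizes.** The SAP gives no power figure for these comparisons, so only the per-arm numbers in section 4.5 can be used. Exact power of the two-sided Fisher test at 0.05 reproduces that table: 0.906 for BV (58 per arm, 50% v 20%), 0.9994 for VVC (50 per arm, 70% v 20%) and 0.906 for Mixed (63 per arm, 35% v 10%). The total is 2×58 + 2×50 + 3×63 = 405. The VVC and Mixed sizes, 50 and 63, are used below. They are per-protocol targets.

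**3. Order does not enter the planned test.** Take constructed counts (absent/mild/moderate/severe) of 20/15/10/5 v 11/14/15/10. Chi-squared gives p = 0.150 and Wilcoxon p = 0.022. After shuffling the severity labels, Chi-squared still gives 0.150, while Wilcoxon gives 0.805.

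**4. The two tests can disagree either way** (constructed counts).

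- 25/15/7/3 v 16/17/10/7. Expected counts per arm are 20.5, 16, 8.5 and 5, so the plan's rule selects Chi-squared. X² = 2 × (4.5²/20.5 + 1²/16 + 1.5²/8.5 + 2²/5) = 4.23 on 3 df, p = 0.24. Wilcoxon rank sum 2248 against an expected 50×101/2 = 2525, tie-corrected SD 137.0, z = -2.02, p = 0.043.
- 30/6/8/19 v 18/20/18/7. Mean ratings are 79/63 = 1.25 and 77/63 = 1.22. X² = 2 × (6²/24 + 7²/13 + 5²/13 + 6²/13) = 19.92, p = 0.0002. Wilcoxon p = 0.84.

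**5. Power under assumed distributions.** The SAP gives no item distributions, so four control distributions were assumed (absent/mild/moderate/severe): .32/.33/.20/.15, .25/.35/.25/.15, .40/.30/.20/.10 and .20/.30/.30/.20. The treated arm is a proportional shift with a common cumulative odds ratio. The planned rule (Chi-squared if all expected counts are at least 5, otherwise exact Fisher) was simulated against tie-corrected Wilcoxon, two-sided 0.05, with 10,000 trials per cell (4,000 for odds ratios 5 and 9 and for 75 per arm). For the imputation rows, 10% of each arm on average was assumed missing at random and set to severe.

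| Odds ratio 2-3 | Planned rule | Wilcoxon | Gap (points) |
|---|---|---|---|
| 50 per arm, none missing | 30-71% | 44-85% | 14-18 |
| 63 per arm, none missing | 37-81% | 54-92% | 11-17 |
| 50 per arm, 10% set to severe | 24-58% | 33-71% | 8-13 |
| 63 per arm, 10% set to severe | 30-69% | 39-79% | 7-13 |

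At an assumed 75 per arm for the mITT population, with none missing, the gap is 8-18 points. At odds ratio 5 it is 1-4 points (1-5 with imputation). At odds ratio 9 it is under 1 point either way. With no treatment effect, both tests reject in 4.6-5.4% of trials.

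**6. Where Wilcoxon does not win.** If only the absent share rises (odds ratio 2-3) and the rest keeps its severity mix, the difference runs from -1 to +11 points. If absent gains 20 points, 12 from mild and 8 from moderate, Wilcoxon is 1-26 points worse. If all 20 come from mild, it is 35-63 points worse.

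**The case against.** The strongest reply is that the problem may never arise. No section states a between-arm test on itching, edema or any other single item. The ratings are summed in sections 3.1 to 3.3, Tables 14.1.13 and 14.2.6 are titled for the severity score, and the table formats are in a companion document that is not at hand. This stands, and the point is conditional for that reason. On the other side, without single items the words about short ordinal endpoints have no evident object.

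A reader might infer something stronger: that the changes/improvements endpoint itself gets an order-blind test, because the four-or-fewer rule mentions only proportions at baseline and endstudy. The document does not support that. Change in a single item has seven values and, read literally, falls under the Wilcoxon rule; Table 14.2.17 shows that a change summary is planned.

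The effect sizes can also be challenged. Section 4.5 expects cure odds ratios of (.70/.30)/(.20/.80) = 9.3 for VVC and (.35/.65)/(.10/.90) = 4.8 for Mixed. These are for the composite cure, not for one item, but they are the only effects in the document, and at such sizes the gap is a few points or less. This stands as a limit on the gain.

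Finally, both tests are valid and neither dominates. Cure of VVC requires all signs and symptoms to resolve, so movement into the absent category is a realistic pattern, and there Wilcoxon may lose. The planned proportions do show direction, and a two-sided Wilcoxon p-value also needs the descriptive data beside it. All of this is fair. It makes the change a preference with a named cost, not the correction of an invalid test.

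**Conclusion.** The point holds in a narrow form, as a cheap improvement. If levels of single 0-3 ratings at a visit are compared between arms, the planned Chi-squared/Fisher test does not test for lower severity, and the plan already uses a more suitable test for longer scales.

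The cost is about 11-18 power points at odds ratios 2-3 with 50-63 per arm and no missing data, about 7-13 with 10% worst-case imputation, a few points at odds ratio 5 and under 1 point at 9. These figures rest wholly on assumed item distributions, proportional shifts and an assumed missing share; other patterns shrink or reverse the gap.

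It should not be read as a threat to the trial's conclusions. Type I error, the primary cure-rate analyses, the summed scores, the Nugent score and change from baseline in a single item are not affected.

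**What to change.** In section 4.7.2, restrict Chi-squared/Fisher to binary and nominal endpoints, such as the discharge characterization, and add a sentence along these lines:

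> Any ordinal secondary endpoint with three or more levels, including a single 0-3 symptom or sign rating compared between arms at a visit, will be compared by the Wilcoxon rank sum test; the proportion of subjects at each level will still be tabulated.

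If no single items are to be tested, deleting *or ordinal* from the four-or-fewer-levels rule settles the matter instead.

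The cost is one sentence and minor programming before unblinding, with no new data and no change to the primary analysis. The downside to accept is less power for non-monotone differences, or when the absent share gains only from mild or from mild and moderate. Keeping the tabulated proportions leaves such patterns visible.
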